7.9.2 Visit Windows

Visit windows are allowed for certain visits per the schedule of assessments. Subject data will not be excluded from analyses due to the subject's failure to comply with the visit schedule. The visit windows for safety variables are described in the following table.

Table 2 Analysis visit window

Visit day interval	Scheduled visit	Analysis visit
Baseline	Baseline prior study	Baseline
Day 1*	Week 1	Day 1
Day 2 – Day 57	Week 5	Week 5 (Day 29)
Day 58 – Day 127	Week 13	Week 13 (Day 85)
Day 128 – Day 211	Week 25	Week 25 (Day 169)
Day 212 – Day 295	Week 37	Week 37 (Day 253)
Day 296 – Day 379	Week 49	Week 49 (Day 337)
Day 380 – Day 463	Week 61	Week 61 (Day 421)
Day 464 – Day 547	Week 73	Week 73 (Day 505)
Day 548 – Day 673	Week 85	Week 85 (Day 589)
Day 674 – Day 841	Week 109	Week 109 (Day 757)
Day 842 – Day 1009	Week 133	Week 133 (Day 925)
Similarly for follow-up visits		

*Day 1 of extension; all day numbers are relative to day 1 of the extension study

In the case of multiple observations at a specific visit, the observation which is closest to the target date will be used. If the observations have the same distance to the target visit, the latest one will be used.

All visit dates and times of dosing will be provided in a listing for each study period.

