5.4.3 Laboratory Assessments

Please refer to [Appendix 2](#) (Liver Safety Monitoring and Assessment) for additional DILI laboratory testing requirements and timing. Routine laboratory assessments for hematology and chemistry will be collected and analyzed at the local laboratory. Laboratory assessments will be assessed at every clinic visit including the safety follow-up visit, see also the Schedule of Assessments (Section V, [Table 1](#)). A maximum of 18 mL of blood will be taken at every visit. See also [Appendix 1](#)

If the results of clinical laboratory tests are outside the normal range and considered clinically significant, the investigator may decide to repeat tests on new samples.

Any changes in laboratory values will be evaluated by the investigator. Clinically important changes from the time of signing the informed consent will be reported as AEs.

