5.4.3.1 Abnormal Liver Function Tests

If laboratory testing for a subject enrolled in a study and receiving study drug reveals an increase of serum aminotransferases (AT) to > 3x ULN, or bilirubin > 2x ULN, at least all four of the usual serum measures (ALT, AST, ALP, and total bilirubin [TBL]) should be repeated within 48 - 72 hours of notification of the test results. See [Appendix 2](#) (Liver Safety Monitoring and Assessment) for additional information on monitoring and assessment of abnormal liver function tests.

Laboratory assessments must be obtained prior to study drug administration.

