5.8 Total Amount of Blood

The total amount of blood for each subject will vary depending on how long they stay on treatment. The maximum amount of blood collected at each clinic visit is approximately 18 ml.

Furthermore, if any laboratory abnormalities are found for a subject, additional blood may be drawn for monitoring.

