7.5.2 Clinical Laboratory Evaluations

Clinical laboratory evaluations (including hematology and serum chemistry) will be summarized for each visit using descriptive statistics. Change from baseline will also be summarized. As a baseline the last assessment before the first day of MDV3100 intake from the prior study will be used. Shift analysis tables will present shift from baseline to the same visits using the NCI-CTCAE grade and laboratory reference range indicator. All clinically significant abnormal laboratory values will be recorded as AEs and graded using NCI-CTCAE guidelines.

Laboratory data will be listed for each test. Each laboratory result will be flagged as low (L), normal, or high (H) at each visit according to laboratory reference ranges. In addition a listing will be presented with the indicated subset of laboratory parameters, if at least one of the following criteria is fulfilled: ALT or AST \geq 3xULN or Bilirubin \geq 2.0 mg/dL (34.2 μ mol/L) or Creatinine $>$ 352 μ mol/L (4.0 mg/dL).

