7.7 Other Analyses

The Eastern Cooperative Oncology Group (ECOG) scale categorized as grade scores 0-5 will be used to assess performance status. The higher grade score of ECOG indicates the worse of the patient's performance. Number and percentage of subjects with grade scores 0-5 will be tabulated at scheduled visits. A shift analysis table showing shifts from baseline to each scheduled visit in ECOG PS grade will be provided. In addition a shift analysis table showing shift from baseline to the highest ECOG PS grade during the extension study will be provided. As a baseline the last assessment before the first day of MDV3100 intake from the prior study will be used.

The ECOG performance status will be provided in a data listing

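### Laboratory CTCAE shifts are tabulated only by visit, from one closest-to-target value per window, so they can understate a subject's worst grade; Safety FU has no analysis visit in Table 2

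*SAP*

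**What the plan says.** **Selection.** SAP 7.9.2 sorts safety observations into adjoining day intervals counted from Day 1 of the extension (Table 2). Within an interval, "In the case of multiple observations at a specific visit, the observation which is closest to the target date will be used". On ties: "If the observations have the same distance to the target visit, the latest one will be used". The section does not say whether unscheduled samples enter the intervals, or whether a scheduled sample takes priority over its repeat.

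**Tabulation.** For laboratory data, SAP 7.5.2 states: "Shift analysis tables will present shift from baseline to the same visits using the NCI-CTCAE grade and laboratory reference range indicator". Protocol 7.5.2 promises the same. No worst-grade laboratory table is listed. For ECOG, SAP 7.7 does add one: a "shift analysis table showing shift from baseline to the highest ECOG PS grade during the extension study will be provided".

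**Off-visit samples.** The protocol foresees them in three places:
- Section 5.4.3.1 and Appendix 2: when aminotransferases exceed 3x ULN or bilirubin exceeds 2x ULN, the liver tests "should be repeated within 48 - 72 hours of notification of the test results". Appendix 2 then asks for testing two to three times a week for confirmed moderate abnormalities.
- Section 5.4.3: for a result outside the normal range that is judged clinically significant, "the investigator may decide to repeat tests on new samples".
- Section 5.8: "if any laboratory abnormalities are found for a subject, additional blood may be drawn for monitoring".

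**Safety FU.** The visit falls 30 days (± 7) after the last dose and includes laboratory tests. Table 2 has no row for it. The table's closing line, "Similarly for follow-up visits", gives no interval or target. It reads most naturally as continuing the 24-week pattern after Week 133.

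**The concern.** Long-term safety is the study's only objective, and laboratory evaluation is part of the primary endpoint. The CTCAE shift table is the one tabulated laboratory grade that does not depend on someone recording an adverse event. Under the selection rule, a single value can stand for as much as 168 days. A high value between visits can be passed over for a value nearer the target, and a raised scheduled value can give way to its own repeat. A reader of the shift table would then see a lower grade than the subject's worst.

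Safety FU raises a separate question of labelling. Its timing follows the last dose, while Table 2 counts from Day 1. Without a stated rule, a programmer could place an off-treatment value in a treatment week or drop it from the by-visit tables.

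**Working it through.** **1. Table 2 reproduced.** Target day = 7 x (week - 1) + 1, which gives Days 29, 85, 169, 253, 337, 421, 505, 589, 757 and 925. Each upper limit should be the midpoint between neighbouring targets, taking Week 157 (Day 1093) as the assumed next visit after Week 133. For example, (29 + 85)/2 = 57, (589 + 757)/2 = 673 and (925 + 1093)/2 = 1009. All ten stated limits match. Window lengths are:

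| Analysis visit | Interval | Days |
|---|---|---|
| Week 5 | 2-57 | 56 |
| Week 13 | 58-127 | 70 |
| Weeks 25 to 73 | e.g. 128-211 | 84 |
| Week 85 | 548-673 | 126 |
| Weeks 109, 133 | 674-841, 842-1009 | 168 |

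**2. Off-visit peak.** Suppose there is a Grade 3 value on Day 700 and a normal value on Day 757. Both fall in the Week 109 window, at distances 57 and 0 from the target. The table shows normal.

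**3. Scheduled value and its repeat.** Let the scheduled sample lie o days from target and the repeat follow k days later. The repeat is chosen when |o + k| <= |o|. For a visit d days early this means k from 1 to 2d. A visit on or after target keeps its scheduled value. The gap k is an assumption: 2 to 3 days after notification plus 0 to 2 days for the result to arrive, which the documents do not give.

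| k (days) | ± 7 window: repeat replaces | ± 3 window (Day 29): repeat replaces |
|---|---|---|
| 2 | 7 of 15 visit days | 3 of 7 |
| 3 | 6 of 15 | 2 of 7 |
| 4 | 6 of 15 | 2 of 7 |
| 5 | 5 of 15 | 1 of 7 |

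These are counts of permitted visit days, not patient frequencies. Checks at target Day 169:
- Visit Day 165, repeat Day 168: distances 4 and 1, so Day 168 is used.
- Visit Day 164, repeat Day 174: a tie at 5, so Day 174 is used.
- Visit Day 169, repeat Day 172: distances 0 and 3, so Day 169 is used and the repeat is left out.

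If unscheduled samples were meant to stay outside the windows, replacement cannot occur, but the off-visit peak in step 2 is still untabulated.

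**4. What the other outputs catch.**
- *Full listing:* every laboratory value in the database, flagged low, normal or high.
- *Threshold listing (SAP 7.5.2):* ALT or AST at or above 3x ULN, bilirubin at or above 2.0 mg/dL, creatinine above 4.0 mg/dL. Every ALT or AST value above 3x ULN that forces a repeat is therefore listed. The bilirubin trigger (2x ULN) is covered wherever the local ULN is at least 2.0/2 = 1.0 mg/dL. The listing covers 4 of the 17 chemistry analytes in protocol 5.4.3.3 and no haematology.
- *AE tables:* any value meeting one of the four criteria in protocol 5.5.1, at its worst severity. A value that prompts a 5.4.3 repeat has already been judged clinically significant, so it belongs here.

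The remainder is an off-visit or replaced graded value that meets none of the four criteria. It could come from numerically triggered liver repeats or from 5.8 monitoring draws.

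**5. Safety FU, if day number alone decides** (last dose + 23 to + 37 days):
- Last dose Day 85: Days 108-122, inside Week 13 (58-127). The Day 85 value is nearer the target, so the FU value is displaced. The same holds for an on-target last dose at each later visit through Week 133, where the window extends at least 42 days past target.
- Last dose Day 29: Days 52-57 fall in Week 5 and are displaced; Days 58-66 are labelled Week 13.
- Last dose Day 120: Days 143-157 are labelled Week 25.

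**The case against.** The strongest reply is that nothing here is an error. The SAP delivers the by-visit shifts that the protocol promises, under an objective, pre-specified rule, in an uncontrolled descriptive study. Laboratory peaks also have an AE route with CTCAE grading, so the ECOG precedent is not a full parallel. This stands, and it limits the point to an improvement.

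Three stronger readings might be inferred, and the documents support none of them:
- *That peaks vanish from the report.* They do not. Step 4 shows where they remain, and the liver values that force repeats are among the best covered.
- *That the rule biases grades downward.* A repeat may be higher or lower than the value it replaces. On 8 to 10 of the 15 visit days in step 3, the scheduled value that prompted the repeat is kept. Only an off-visit value higher than the one selected leads to understatement, and how often that happens is unknown.
- *That Safety FU values will be mislabelled.* Safety FU is a distinct scheduled visit and Table 2 has a scheduled-visit column, so the CRF label may be what decides. Subjects who roll over to the follow-on study need no Safety FU visit. The SAP also counts events starting within 30 days of last dose as treatment-emergent, so it does not treat that period as wholly separate from treatment.

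The TLF specifications and the EDC manual are not available and may settle some of this. Even so, SAP 7.1 cites the TLF specifications for formats. A rule for choosing or labelling values belongs in the SAP.

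**Conclusion.** The point holds in a limited form. The planned laboratory shift tables take one value per window regardless of grade and can understate a subject's worst CTCAE grade. No other laboratory summary table corrects this for values that meet no AE criterion. Such values appear only in listings and, for most analytes, only in the full listing.

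No patient frequency and no net direction of replacement can be given, because the documents do not say how often unscheduled tests occur or whether they enter the windows. The step 3 counts assume one repeat and a 2- to 5-day gap.

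The missing Safety FU entry in Table 2 is a plain omission. Its consequences in step 5 hold only if day number alone decides. Overall this is a cheap improvement that serves the study's only objective; it does not undermine the planned analysis.

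**What to change.** - **SAP 7.5.2:** add a shift table from baseline to the worst post-Day-1 CTCAE grade, in each direction where an analyte is graded both ways. Use all scheduled and unscheduled values in the database through 30 days after last dose, matching the TEAE period in SAP 6.2. Because the ± 7 window allows Safety FU up to day 37, show values taken after day 30 separately or flag them.
- **SAP Table 2:** give Safety FU, identified by its CRF visit label, its own analysis visit outside the week windows, and say what the closing line covers.
- Leave the other week windows and the by-visit tables unchanged.

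The cost is some SAP wording and one extra table, agreed before hard lock. The new table may show less favourable grades than the by-visit tables. Liver results held only on the LA-CRF or another document may not be in the database, so the table could still miss them; the SAP should say whether they are included.
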